Appendix 5: Flowchart for Emergency Response to Severe Adverse Events

Appendix 6. Overview of the Radiology Subgroup Study

The Radiology Subgroup Study involves conducting baseline and endpoint head MRI examinations on the patients enrolled in this study.

Study objective

The primary objective of this study is to collect patients' radiological data, objectively assess the efficacy of the drug, assist in diagnosis and treatment, and determine endpoint events.

Study time point

The study is divided into two time points: baseline MRI examination and endpoint examination.

Baseline examination (prior to randomization)

Prior to randomization, screen acute stroke patients (within 72 h after onset).

Exclude lesions such as cerebral hemorrhage, vascular malformation, tumor, and abscess.

Endpoint examination (Day 90 of randomized treatment)

Compare with the baseline examination and observe the continuous changes in the radiological presentation of patients.

Identify new infarctions or hemorrhagic lesions (primary endpoints).

Identify other changes (such as alterations in large cerebral vessels).

Examination equipment requirements

Above 1.5 T

Equipped with echo planar imaging for conducting DWI.

Capable of performing T2*GRE sequence scans.

Capable of ensuring the use of the same equipment for both baseline imaging examinations and imaging examinations at the 90 day follow-up.

[figure not shown]
Examination requirements

The patient's position and orientation should strictly adhere to the requirements outlined in this manual. Endpoint examinations should ensure consistency in cross-sectional scanning planes and slice thickness with baseline examinations.

[figure not shown]
1. Patient positioning requirements: The horizontal line passes through both eyebrows, and the vertical line passes through the midline of the nose. As shown in the figure below.

[figure not shown]
2. Three-axis orientation: As shown in the figure below.

[figure not shown]
Coronal T1WI: As shown in the figure below.

[figure not shown]
4. Cross-sectional orientation: As shown in the figure below.

[figure not shown]
5. Cross-sectional DWI: The scanning range covers the entire brain, and scans with b-values of 0 and 1,000 should be performed separately. The slice thickness is 5 mm, with an interslice gap of 30% (i.e., 1.5 mm).

[figure not shown]
A Randomized, Double-blind, Placebo-controlled, Multicenter Clinical Study of Tongxinluo Capsule in the Treatment of Ischemic Stroke

6. Cross-sectional T2WI + FLAIR + T2*GRE: The scanning range, orientation lines, slice thickness, gap, and center for each cross-sectional scan should be consistent with those for DWI scans.

7. MRA: Utilizing the Time-of-Flight (TOF) technique, scan the entire brain. Image post-processing: MIP reconstruction, left-right and top-bottom rotation, with a reconstruction angle of 12 degree. As shown in the figure below

8. Collection of radiological data

The collected radiological images are saved in DICOM format, and the digitized images are stored on rewritable magneto-optical disks provided by the project team. Periodically, the

collected disks are sent to the Central Imaging Evaluation Laboratory based on the specific circumstances of each center.

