7.1 Clinical observation endpoints

7.1.1 Primary efficacy endpoint

Improvement in self-care ability (proportion of patients with mRS score ≤1) after 90 days of treatment

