9.1 Efficacy determination criteria

9.1.1 Primary efficacy assessment

• The proportion of patients with improvement in activities of daily living 90 days after treatment (mRS score ≤1): mRS ≤1 indicates complete or substantial recovery of activities of daily living, representing a favorable prognosis. Comparison of the proportion of patients with favorable prognosis in the treatment group and the control group 90 days after randomization;

9.1.2 Secondary efficacy assessment:

- Improvement in neurological deficit, i.e., the proportion of patients with NIHSS ≤1 or NIHSS improved by 4 points or more: NIHSS score ≤1 or reduction of ≥4 points is considered effective; compare the proportion of effective and ineffective patients and continuous changes of NIHSS in the treatment group and the control group after 90 days of randomized treatment;
- Proportion of patients with BI index ≥85: BI score ≥85 indicates the ability to live
 independently. Compare the proportion of patients able to live independently between
 the treatment group and the control group 90 days of randomized treatment, as well as
 continuous changes in BI scores between the two groups;
- Disability rate, defined as the proportion of patients with an mRS score ≥3: An mRS score ≥3 indicates the inability to live independently. Compare the percentage of disabled patients between the treatment group and the control group 90 days of

randomized treatment:

- Continuous changes in mRS scores: Compare the changes in mRS scores between the treatment group and the control group at different visit points, including baseline, 7 d, discharge, and 90 d;
- Incidence of ischemic cerebrovascular events during the follow-up period: The
 proportion of ischemic stroke or TIA within 90 days of randomized treatment, or
 newly occurring ischemic lesions detected on MRI at the last visit, will be assessed as
 a group or separately;
- Incidence of combined vascular events during the follow-up period: The cumulative
 incidence of newly occurring combined vascular events within 90 days of randomized
 treatment will be assessed as a group or separately;

Definition of combined vascular events: Consist of any type of stroke (ischemic stroke, hemorrhagic stroke), TIA, myocardial infarction, and vascular death.

Vascular death: Hemorrhagic death of any organ or fatal pulmonary embolism.

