5.1 Primary effect index

Improvement of daily life ability 90 days after treatment (ratio of mRS score ≤1)

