5.2 Secondary effect index

1. Improvement of neurological deficits (ratio of NIHSS≤1 or improve 4 score or more);

Improvement of neurological deficits (ratio of NIHSS≤1 or improve 4 score or more): It is effective for NIHSS≤1 or reducing 4 points or more; compare the ratio of efficacy and inefficacy and the continuous change of NIHSS between treatment group and control group 90 days after random treatment;

2. Improvement of daily life ability (ratio of BI index ≥85);

Ratio of patients with BI index≥85: BI score≥85 indicates the patient with ability of independent living; compare the ratio of patient with ability of independent living and continuous change of BI between treatment group and control group at 90 days after random treatment;

3. Disability rate (ratio of mRS score \geq 3)

mRS≥3 indicates the patient without self-care ability; compare the disability rate between treatment group and control group at 90 days after random treatment;

4. Continuous change of mRS score

Compare change of mRS score at baseline, 7d, discharge day and 90d between treatment group and control group;

5. Incidence of ischemic cerebrovascular diseases during follow-up period;

Ratio of ischemic stroke or TIA within 90 days after random treatment, or ratio of new ischemic focus detected by MRI during the last visit, and take this kind of patients as a group for evaluation or respective evaluation:

6. Incidence of combined vascular events during follow-up period;

Accumulated ratio of patients having newly combined vascular events within 90 days after random treatment;

Definition of combined vascular events: Include any type of stroke (ischemic stroke and hemorrhagic stroke), TIA, myocardial infarction and vascular death.

Vascular death: Hemorrhagic death or fatal pulmonary embolism of any organ.

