7.2 Demographic description and baseline description (FAS)

Table 7.2.1.1 Demographic description (FAS)

Item	Index	Total	Treatment group Control group
	N(Missing)		
Age (year)	Mean(SD)		
	Median		
	Q1,Q3		
	Min,Max		
	Statistics		
	P Value		
Sex	Male n(%)		
	Female n(%)		
	N (Missing)		
	Statistics		
	P value		
Marital status	Unmarried n(%)		
	Married n(%)		
	N (Missing)		
	Statistics		
	P value		
Body height (cm)	N(Missing)		
	Mean(SD)		
	Median		
	Q1,Q3		
	Min,Max		
	Statistics		
	P value		
Body weight (kg)	N(Missing)		
	Mean(SD)		
	Median		
	Q1,Q3		
	Min,Max		
	Statistics		
	P value		
BMI (Kg/m^2)	N(Missing)		
	Mean(SD)		
	Median		
	Q1,Q3		
	Min,Max		
	Statistics		

Item	Index	Total	Treatment group Control group
	P value		
Nationality	Han n(%)		
-	Others n(%)		
	N (Missing)		
	Statistics		
	P value		
Job category	Manual labor n(%))	
	Non-manual labor		
	n(%)		
	N (Missing)		
	Statistics		
	P value		

Table 7.2.1.2 Medical history (FAS)

Item	Index	Total	Treatment group Control group
	Cerebral infarction n(%)		
Diagnosed with	Acute phase n(%)		
Western medicine			
	N (Missing)		
	Statistics		
	P value		
	Atherothrombotic stroke n(%)	
TOAST type	Cardioembolism n(%)		
	Small artery occlusive stroke	n(%)	
	Ischemic stroke caused by oth	ner	
	reasons n(%)		
	Ischemic stroke of unknown	n causes	
	n(%)		
	N (Missing)		
	Statistics		
	P value		
	≤12h n(%)		
Course of disease	12-48h n(%)		
	48-72h n(%)		
	N (Missing)		
	Statistics		
	P value		
	First onset n(%)		
First onset	Recurrence n(%)		
/recurrence			
	N (Missing)		
	Statistics		
	P value		

Table 7.2.1.3 Past history (FAS)

Item	Index	Total	Treatment group Control group
Smoking history	With n(%)		
	Without n(%)		
	Quit smoking		
	N (Missing)		
	Statistics		
	P value		
History of alcohol	With n(%)		
intake			
	Without n(%)		
	n(%)		
	N (Missing)		
	Statistics		
	P value		
History of	Non-menopause n(%)		
menopause			
	Post-menopause n(%)		
	Not applicable n(%)		
	N (Missing)		
	Statistics		
	P value		
	With n(%)		
Drug allergy	Without n(%)		
history			
	N (Missing)		
	Statistics		
	P value		
	With n(%)		
Past history	Without n(%)		
	N (Missing)		
	Statistics		
	P value		

Table 7.2.1.4 Imaging examination (FAS)

Item	Index	Total	Treatment group Control group
	With n(%)		
Cerebral infarction	Without n(%)		
	N (Missing)		
	Statistics		
	P value		
	With n(%)		
Hemorrhagic	Without n(%)		
impression			
	N (Missing)		
	Statistics		
	P value		

Table 7.2.1.5 Therapeutic condition (FAS)

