7.3.6 Secondary effect index – continuous change of mRS score

Table 7.3.6.1 Continuous change of mRS score (FAS)

Item	Index	Treatment group	Control group
	N(Missing)		
Baseline mRS score	Mean(SD)		
	Median		
	Q1,Q3		
	Min, Max		
	Statistics		
	P value		
	N(Missing)		
mRS score at 7 days after treatment	Mean(SD)		
•	Median		
	Q1,Q3		
	Min, Max		
	Statistics		
	P value		
	N(Missing)		
Change of mRS score at 7 days after treatment comparing with baseline	Mean(SD)		
r	Median		
	Q1,Q3		
	Min, Max		
	Statistics		
	P value		
	95%CI		
	Statistics		
	P value		
	N(Missing)		
mRS score at discharge day	Mean(SD)		
5	Median		
	Q1,Q3		
	Min, Max		
	Statistics		
	P值 P value		
	N(Missing)		
Comparison of mRS score at discharge			
day comparing with baseline	,		
	Median		
	Q1,Q3		
	Min, Max		
	Statistics		

Study No.: Document No.:

Item	Index	Treatment group	Control group
	P value		
	95%CI		
	P value		
	N(Missing)		
mRS score at 90 days after treatment	Mean(SD)		
	Median		
	Q1,Q3		
	Min, Max		
	Statistics		
	P value		
	N(Missing)		
Changes of mRS score at 90 days after	er Mean(SD)		
treatment comparing with baseline			
	Median		
	Q1,Q3		
	Min, Max		
	Statistics		
	P value		
	95%CI		
	Statistics		
	P value		

Table 7.3.6.2 Continuous change of mRS score (PPS)

The same as above

7.3.7 Secondary effect index – incidence of ischemic cerebrovascular diseases during follow-up period Table 7.3.7.1 Inter-group comparison of incidence of ischemic stroke within 90 days after treatment

		FAS		PPS	
		Treatment		Treatment	
Item	Index	group	Control group	group	Control group
	With n(%)				
	Without n(%)				
Have ischemic stroke within	N (Missing)				
90 days after treatment					
	Statistics				
	P value				

Table 7.3.7.2 Inter-group comparison of TIA incidence within 90 days after treatment

The same as above

Table 7.3.7.3 Inter-group comparison of ratio of new ischemic focus detected by MRI at last visit

		FAS		PPS	
		Treatment		Treatment	_
Item	Index	group	Control group	group	Control group
	With n(%)				_
	Without n(%)				
New ischemic focu	s detected N (Missing)				
by MRI at the last v	risit				
	Statistics				
	P value				

Table 7.3.7.4 Inter-group comparison of incidence of ischemic cerebrovascular disease during follow-up period

		FAS		PPS	
		Treatment		Treatment	
Item	Index	group	Control group	group	Control group
	With n(%)				
Have ischemic cerebrovascular disease during visit	Without n(%)				
	N (Missing)				
	Statistics				
	P value				

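### Appendix 6 labels Day-90 MRI lesions as primary endpoints without saying of what, and the SAP plans no between-arm comparison of the haemorrhagic reading

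*Combined protocol and SAP*

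**What the plan says.** **The label.** Appendix 6 describes the Radiology Subgroup Study and gives it an aim of its own: "The primary objective of this study is to collect patients' radiological data, objectively assess the efficacy of the drug". Under the endpoint examination on Day 90 it lists "Identify new infarctions or hemorrhagic lesions (primary endpoints". It adds no hypothesis, alpha or sample size for these lesions.

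**The trial primary.** Protocol 7.1.1 has "Improvement in self-care ability (proportion of patients with mRS score ≤1) after 90 days of treatment" and SAP 5.1 has "Improvement of daily life ability 90 days after treatment (ratio of mRS score ≤1". The synopsis, protocol 9.1.1 and 12.2.3, SAP 6.2.4 and SAP Table 7.3.2.1 agree. The sample size (protocol 4.2, SAP 4.4) is built on that endpoint alone.

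**The infarct reading.** Protocol 9.1.2 includes "newly occurring ischemic lesions detected on MRI at the last visit" within the secondary endpoint on ischaemic cerebrovascular events. SAP 5.2 does the same with "ratio of new ischemic focus detected by MRI during the last visit". The SAP has a table for it, 7.3.7.3: "Inter-group comparison of ratio of new ischemic focus detected by MRI at last visit".

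**The haemorrhagic reading.** Protocol 8.4 includes a T2* sequence in the Day-90 MRI at radiology-subgroup centres, and protocol section 14 sends the images for central reading by two people. In the SAP, a haemorrhagic finding on imaging appears in two places. One is the baseline section ("Table 7.2.1.4 Imaging examination (FAS"). The other is Tables 7.5.5.3 and 7.5.5.4, where it divides patients into subgroups for the mRS analysis.

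**The concern.** There are two linked problems.

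First, the word primary is attached to an MRI finding in one place and to mRS ≤1 everywhere else, and Appendix 6 does not say which study it means. A label that can be read two ways is best settled before unblinding.

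Second, Appendix 6 names two kinds of lesion and the SAP follows only one. Images are acquired and read centrally in part to find new haemorrhagic lesions, yet no planned table says how many occurred in each arm. For a treatment given for 90 days on top of standard stroke care, new bleeding on MRI is a result a reader would expect to see, even if only descriptively. As planned, an imbalance in silent lesions could be missed.

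**Working it through.** **1. Does the sample size leave room for an MRI primary?** Inputs from protocol 4.2: 40% against 47%, two-sided α = 0.05, power 80%, 1:1 allocation, 20% dropout.

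n per arm = [z₀.₉₇₅ √(2p̄q̄) + z₀.₈₀ √(p₁q₁ + p₂q₂)]² / (p₂ − p₁)², with p̄ = 0.435.

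- √(2 × 0.435 × 0.565) = 0.7011 and √(0.2400 + 0.2491) = 0.6994
- (1.960 × 0.7011 + 0.8416 × 0.6994)² / 0.07² = 3.852 / 0.0049 ≈ 786.2, so 787 per arm
- 787 / (1 − 0.20) = 983.75, so 984 per arm and 1,968 in total

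Both stated figures are reproduced. They spend the whole alpha on mRS ≤1, and nothing is set aside for MRI.

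**2. Where does each MRI finding go?**

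| Day-90 finding | Appendix 6 | Protocol 9.1.2 / SAP 5.2 | Between-arm outcome table in the SAP |
|---|---|---|---|
| New infarct | labelled primary | part of a secondary endpoint | 7.3.7.3, and within 7.3.7.4 |
| New haemorrhagic lesion | labelled primary | absent | none |

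The baseline imaging table does carry a between-group P value, but it describes the state at entry. Haemorrhage on head imaging is also an exclusion criterion (protocol 5.2, SAP 4.5.2), so few positive cases are expected there. The subgroup tables use the finding to divide patients, not as an outcome.

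**3. What other routes catch bleeding?**

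- Haemorrhagic stroke is a component of the combined vascular endpoint. SAP 7.3.8 lists no table for it alone.
- Protocol 10.4.2 makes any haemorrhagic event reportable as AE/SAE. SAP 6.2.5 compares adverse event incidences, although Table 7.4.1.1 shows only summary rows.
- MRI is not among the safety indicators in protocol 7.2 or SAP 5.3. Neither document says that a silent lesion found by the central readers becomes an adverse event.

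What remains uncovered is the clinically silent lesion seen only on MRI.

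**4. Could such lesions be common?** The guideline in protocol Appendix 7 puts haemorrhagic transformation at 8.5% to 30% and symptomatic cases at 1.5% to 5%. If both are percentages of all ischaemic strokes, pairing like ends gives a silent share of 1 − 1.5/8.5 = 82% and 1 − 5/30 = 83%. The extreme pairings give 1 − 5/8.5 = 41% and 1 − 1.5/30 = 95%. These figures describe haemorrhagic transformation in general, not new lesions at Day 90 in this trial. They show only that silent lesions need not be rare.

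**5. Illustration of multiplicity.** Suppose MRI results were also claimed as trial primaries, each at one-sided 0.025, independent and unadjusted. The chance of at least one false claim of benefit would be 1 − 0.975² = 4.9% with one combined MRI endpoint, or 1 − 0.975³ = 7.3% with two separate ones, against 2.5%. No document plans this.

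**The case against.** The strongest reply is that the label belongs to the substudy. Appendix 6 is headed as an overview of the Radiology Subgroup Study, and its own primary objective, a few lines above, can only be that of the substudy, since the trial's objective is stated in protocol section 2. On that reading nothing conflicts. This is plausible and may well be what was meant. It stands as a reason to treat the problem as an unclear label, but not as a reason to leave the label as it is: Appendix 6 does not say so, and no analysis is set out for substudy primaries.

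A reader might infer that the trial has competing primary endpoints and an inflated error rate, for example 1 − 0.95³ = 14.3% two-sided. The documents do not support that. The SAP governs the analysis and is unambiguous: mRS ≤1 is primary, and the MRI ischaemic focus is secondary. An MRI result presented as the trial's primary success would contradict the SAP, the synopsis and protocol 7.1.1. The two-sided figure also counts results in the harmful direction, which could not support a claim of benefit.

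A reader might also infer that bleeding is never compared, or would go unreported. That goes too far as well. Clinical haemorrhagic stroke is in the composite, an independent committee reviews vascular events, and haemorrhagic events enter the adverse event analysis and listings.

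Finally, the guideline in Appendix 7 reports no statistical difference in prognosis with asymptomatic transformation, and calls the meaning of microhaemorrhage for thrombolytic or antithrombotic therapy unclear. That limits the weight of the point. It does not explain why a planned reading has no planned table.

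**Conclusion.** The point holds in two limited parts. The Appendix 6 label is unclear about which study it refers to and should be reconciled with the single trial primary, mRS ≤1 at 90 days. The Day-90 haemorrhagic reading has no planned between-arm outcome comparison, which leaves clinically silent MRI-only lesions unexamined.

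The second part matters more, because it changes what the trial can say about bleeding. Its size cannot be given: the number of patients in the radiology subgroup is not stated, so the precision of any comparison is unknown. The sample size and alpha are unaffected, and the 4.9% to 7.3% figures are illustrative only. The conclusion assumes that no other document turns centrally read silent lesions into adverse events, since neither the protocol nor the SAP does.

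**What to change.** - **Appendix 6.** Replace the bracketed label with: main outcomes of the radiology substudy; not primary endpoints of the trial, whose sole primary is mRS ≤1 at 90 days.
- **SAP.** Add one table: new haemorrhagic lesion on Day-90 MRI versus baseline, from the central reading, in radiology-subgroup patients with both scans. Give n/N by arm, the difference and its 95% CI, and report it descriptively under safety. The flowchart notes allow the subgroup's baseline MRI up to 3 days after randomisation, while Appendix 6 places it before. A footnote should therefore count the patients whose baseline scan came after randomisation.

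**Cost.** One phrase and one extra table, from readings already planned. There are no new data, and no change to sample size or alpha. The table may turn out imprecise, depending on the size of the subgroup.

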Appendix 7: Guidelines for the Diagnosis and Treatment of Acute Ischemic Cerebrovascular

Disease in China 2010

Guidelines for Diagnosis and Treatment of Acute Ischemic Stroke in China 2010

Acute ischemic stroke (cerebral infarction) is the most common type of stroke, accounting for 60% to 80% of all strokes. The time division for its acute phase is not yet unified, generally referring to the first two weeks after onset. The management of acute ischemic stroke should emphasize early diagnosis, early treatment, early rehabilitation, and early prevention of recurrence. The Chinese Stroke Society initiated the compilation of the Chinese Guidelines for the Prevention and Treatment of Cerebrovascular Diseases at the end of 2002. In early 2005, it was officially approved by the Ministry of Health for nationwide promotion. In early 2007, the People's Medical Publishing House formally published the first edition of the Chinese Guidelines for the Prevention and Treatment of Cerebrovascular Diseases. It played a positive role in standardizing the diagnosis and treatment of cerebrovascular diseases in China. Due to the continuous publication of new study evidence in recent years, the first edition of the guidelines has also received multiple suggestions for improvement during its usage. Therefore, the Chinese Society of Neurology entrusted the Chinese Stroke Society to revise the first edition of the guidelines. For clinical convenience, this edition of the guidelines includes the entire diagnostic and treatment process for acute ischemic stroke after onset. The writing group, after reviewing relevant study evidence, soliciting opinions from various sources, and engaging in thorough discussions to reach a consensus, has formulated recommendations, with the aim to assist clinicians in choosing the currently more favorable diagnostic and treatment strategies for stroke patients. In clinical practice, physicians should tailor individualized treatments based on the principles of these guidelines, new developments, and specific conditions of the patients.

I. Revision Principles

1. Guided by the principles of evidence-based medicine, the revision is made by referencing international standards, and considering national conditions, feasibility, the experience of using the first edition, and new study evidence. The strength of recommendation and evidence grade are based on international guidelines and common standards, taking into account national conditions and practicality.

Ischemic Stroke

- 2. For each treatment measure or clinical issue, a summary and analysis of current study evidence (literature search up to November 2009) are conducted first. Recommendations are then provided based on the evidence grade and consensus.
- 3. Recommendations are based on the most reliable evidence whenever possible (such as Grade A evidence). In the absence of high-level evidence, the best available evidence is considered, and consensus is reached through thorough discussion.
- 4. For commonly used therapies in China, guided by the principles of evidence-based medicine, consensus is reached by fully considering national conditions and experience. Attention is paid to balancing efficacy, risks, cost, and ease of use, among other factors.
- II. Standards for Strength of Recommendations and Evidence Grade (including therapeutic and diagnostic measures)
- 1. Strength of recommendation (divided into 4 levels, with Level I being the strongest and Level IV being the weakest): Level I: Based on Grade A evidence or expert consensus with high consistency; Level II: Based on Grade B evidence and expert consensus; Level III: Based on Grade C evidence and expert consensus; Level IV: Based on Grade D evidence and expert consensus.
- 2. Evidence grade for therapeutic measures (divided into 4 grades, with Grade A being the highest and Grade D being the lowest): Grade A: Meta-analysis or systematic review of multiple randomized controlled trials (RCTs); multiple RCTs or one RCT with sufficient sample size (high quality); Grade B: At least one high-quality RCT; Grade C: Non-randomized but welldesigned controlled trials, or well-designed cohort studies or case-control studies; Grade D: Series case analysis without concurrent control or expert opinion.
- 3. Evidence grade for diagnostic measures (divided into 4 grades, with Grade A being the highest and Grade D being the lowest): Grade A: Multiple prospective cohort studies or one prospective cohort study with sufficient sample size, utilizing reference (gold) standards, and blinded assessment (high quality); Grade B: At least one prospective cohort study or welldesigned retrospective case-control study, utilizing gold standards and blinded assessment (higher quality); Grade C: Retrospective, non-blinded controlled studies; Grade D: Series case analysis without concurrent control or expert opinion.

I Pre-hospital Management

The key to pre-hospital management is to promptly identify suspected stroke patients and transport them to the hospital as quickly as possible.

i. Pre-hospital Identification of Stroke

If a patient suddenly experiences the following symptoms, the possibility of a stroke should be considered: 1 Weakness or numbness in one side of the body (with or without facial

Ischemic Stroke

involvement); ② Numbness on one side of the face or distortion of commissure; ③ Slurred speech or difficulty understanding language; ④ Gaze deviation of both eyes to one side; ⑤ Loss or blurred vision in one or both eyes; ⑥ Dizziness with vomiting; ⑦ Unusual and severe headache with vomiting; ⑧ Impaired consciousness or seizures.

ii. On-site Management and Transportation

On-site emergency personnel should promptly conduct a brief assessment and necessary first aid, including: ① Managing airway, breathing, and circulation issues; ② Monitoring the heart; ③ Establishing intravenous access; ④ Administering oxygen; ⑤ Assessing for hypoglycemia.

Avoid: ① Administering sugar-containing fluids to non-hypoglycemic patients; ② Excessively lowering blood pressure; ③ Large-volume intravenous infusions.

Quickly obtain a brief medical history, including: ① Time of symptom onset; ② Recent medical history; ③ Past medical history; ④ Recent medication history.

Patients should be promptly transported to the nearest qualified hospital (with the capability of 24 h emergency CT scans).

Recommendation: For patients who suddenly experience the above symptoms and are suspected of having a stroke, a brief assessment and emergency treatment should be conducted, and they should be promptly transported to the nearest qualified hospital (Level I recommendation).

II. Emergency Room Diagnosis and Treatment

Due to the narrow treatment window for acute ischemic stroke, timely assessment of the condition and diagnosis are crucial. Hospitals should establish a rapid pathway for the diagnosis and treatment of strokes, prioritizing the handling and admission of stroke patients whenever possible.

i. Diagnosis

- 1. Medical history collection and physical examination: Conduct medical history collection and physical examination as soon as possible (see relevant content in Section IV).
- 2. Diagnostic and assessment steps: (1) Is it a stroke? Pay attention to the presentation form and onset time. Exclude brain lesions caused by conditions such as head trauma, poisoning, postictal state, tumor-related stroke, hypertensive encephalopathy, abnormal blood glucose, encephalitis, and severe dysfunction of vital organs. Conduct necessary laboratory tests (see relevant content in Section IV). (2) Is it an ischemic or hemorrhagic stroke? Unless there are special reasons preventing the examination, all suspected stroke cases should undergo prompt neuroimaging (CT or MRI) to rule out hemorrhagic stroke and establish the diagnosis of

ischemic stroke. (3) Is the patient suitable for thrombolytic therapy? Is the onset time within 4.5 or 6 h? Are there indications for thrombolysis? (See relevant content in Section IV).

ii. Management

Close monitoring of basic life functions such as airway and breathing; cardiac monitoring and treatment of cardiac abnormalities; blood pressure and temperature regulation. Emergent situations that require immediate attention: Increased intracranial pressure, severe blood pressure abnormalities, abnormal blood glucose and temperature, seizures, etc. (see relevant content in Section IV).

Recommendation: Perform a rapid diagnosis of suspected stroke patients according to the above diagnostic steps. Complete assessments such as brain CT within 60 min of arriving at the emergency room if possible and make treatment decisions promptly (Level I recommendation).

iii. Stroke Unit

A stroke unit is an organized medical management model for stroke inpatients, combining various independent methods of traditional stroke treatment such as drug therapy, physical rehabilitation, speech training, psychological rehabilitation, and health education into a comprehensive treatment system. A Cochrane systematic review (including 23 trials, 4,911 patients) has confirmed that stroke units significantly reduce the mortality and disability rates of stroke patients.

Recommendation: Hospitals admitting stroke patients should establish stroke units whenever possible. All acute ischemic stroke patients should be admitted to stroke units as early as possible (Level I recommendation, Grade A evidence) or neurology wards (Level II recommendation) for treatment.

IV Diagnosis and Treatment in the Acute Phase

i. Assessment and Diagnosis

Assessment and diagnosis of stroke include: medical history and physical examination, imaging tests, laboratory tests, disease diagnosis, and etiological classification.

(i) Medical History and Physical Examination

1. Medical history collection: Inquiring about the time of symptom onset is crucial. Other information includes the characteristics and progression of neurological symptoms, cardiovascular risk factors, medication history, drug abuse, migraines, seizures, infections, trauma, and pregnancy history.

- 2. General physical examination and neurological examination: After assessing airway, breathing, and circulation functions, proceed immediately with a general physical examination and neurological examination.
- 3. Stroke scales can be used to assess the severity of the condition. The commonly used scales include: (1) Chinese Stroke Patient Clinical Neurological Deficit Severity Scale (1995). (2) National Institutes of Health Stroke Scale (NIHSS), the most widely used scale internationally. (3) Scandinavian Stroke Scale (SSS).
 - (ii) Examination of Brain Lesions and Vascular Lesions
- 1. Brain lesion examination: (1) Plain CT scan: Emergency plain CT scan can accurately identify the majority of intracranial hemorrhages and help differentiate non-vascular lesions (such as brain tumors). It is the preferred imaging method for patients suspected of having a stroke. (2) Multi-modal CT: Perfusion CT can differentiate reversible from irreversible ischemia, thus identifying the ischemic penumbra. However, its role in guiding the treatment of acute cerebral infarction is not yet certain. (3) Standard MRI (T1-weighted, T2-weighted, and proton density) is significantly superior to plain CT in identifying acute small infarcts and posterior fossa infarcts. It can identify subclinical infarcts, does not involve ionizing radiation, and does not require contrast agents containing iodine. However, it has limitations, including higher cost, longer examination time, and contraindications in patients (with cardiac pacemakers, metal implants, or claustrophobia). (4) Multi-modal MRI includes Diffusion-Weighted Imaging (DWI), Perfusion-Weighted Imaging (PWI), Fluid-Attenuated Inversion Recovery (FLAIR), and Gradient Recalled Echo (GRE) imaging. DWI can detect ischemic lesions within minutes of symptom onset and can early determine the size, location, and time of the infarct. It is more sensitive for early detection of small infarcts compared to standard MRI. PWI can display the cerebral hemodynamic status. The mismatch between diffusion and perfusion (PWI showing a low perfusion area without a corresponding diffusion abnormality of the same size) suggests the possible presence of ischemic penumbra. However, the current evidence for routine use in selecting thrombolytic therapy patients is not yet sufficient. The gradient echo sequence can reveal asymptomatic microhemorrhage that CT cannot indicate, but the significance for thrombolytic or antithrombotic therapy is not yet clear.
- 2. Vascular lesion examination: Intracranial and extracranial vascular lesion examination helps to understand the pathogenesis and etiology of stroke, guiding the selection of treatment strategies. Commonly used examinations include carotid duplex ultrasonography, transcranial Doppler (TCD), magnetic resonance angiography (MRA), CT angiography (CTA), and digital subtraction angiography (DSA).

Carotid duplex ultrasonography is helpful in detecting extracranial carotid vascular lesions, especially stenosis and plaques. Transcranial Doppler (TCD) can examine intracranial blood flow and microemboli, and monitor treatment effects, but its performance is significantly influenced by the operator's technical proficiency and the presence of bone windows.

MRA and CTA can provide information about vascular occlusion or stenosis. With DSA as the reference standard, the sensitivity and specificity of MRA for detecting stenosis in the vertebral and extracranial arteries are 70% to 100%. MRA can demonstrate proximal occlusion or stenosis in large intracranial vessels, but it may have limitations in displaying distal or branching vessels clearly.

DSA has the highest accuracy and remains the gold standard for vascular lesion examination, but its main drawbacks include invasiveness and certain risks.

(iii) Laboratory and Imaging Examination Selection

For suspected stroke patients, routine laboratory tests should be conducted to exclude stroke mimics or other etiologies.

Tests that should be conducted for all patients include: ① Plain brain CT or MRI; ② Blood glucose, blood lipid, liver and kidney function, and electrolytes; ③ Electrocardiogram and cardiac ischemia markers; (4) Complete blood count, including platelet count; (5) Prothrombin time (PT), international normalized ratio (INR), and activated partial thromboplastin time (APTT); ⑥ Oxygen saturation; ⑦ Chest X-ray.

Tests that may be considered for some patients when necessary include: ① Toxicology screening; ② Blood alcohol levels; ③ Pregnancy test; ④ Arterial blood gas analysis (if hypoxia is suspected); ⑤ Lumbar puncture (suspected subarachnoid hemorrhage not visible on CT or suspicion of stroke secondary to infectious disease); ⑥ Electroencephalogram (suspected seizure).

(iv) Diagnosis

The diagnosis of acute ischemic stroke can be based on: (1) Acute onset of symptoms; (2) Focal neurological deficits, with a minority presenting with global neurological deficits; (3) Symptoms and signs lasting for several hours or longer (for thrombolysis, patients should meet specific criteria); (4) Brain CT or MRI ruling out hemorrhage and other lesions; (5) Brain CT or MRI revealing responsible infarct lesions.

(v) Etiological Classification

Classifying the etiology of acute ischemic stroke in patients helps determine prognosis, guide treatment, and select secondary prevention measures. The widely used TOAST classification system internationally categorizes ischemic stroke into five types: large-artery atherosclerosis, cardioembolic, small-vessel occlusion, other determined etiology, and undetermined etiology.

(vi) Diagnostic Process

Diagnostic process for acute ischemic stroke should include the following 5 steps: (1) Is it a stroke? Exclude non-vascular diseases. (2) Is it an ischemic stroke? Perform a brain CT or

MRI scan to rule out hemorrhagic stroke. (3) Severity of stroke? Assess based on the neurological deficit scale. (4) Is thrombolytic therapy possible? Verify indications and contraindications (refer to relevant information on thrombolysis). (5) Etiologic classification? Refer to the TOAST criteria and determine the etiology based on medical history, laboratory results, brain lesions, and vascular lesions.

Recommendation: (1) Head CT or MRI scan is recommended for all suspected stroke patients (Level I recommendation). (2) Prior to thrombolytic and other treatments, a head CT scan is recommended (Level I recommendation). (3) The aforementioned hematological, coagulation, and biochemical tests are recommended (Level I recommendation). (4) All stroke patients should undergo ECG examination (Level I recommendation). (5) Assess the severity of the condition using the neurological deficit scale (Level II recommendation). (6) Vascular lesion examination is recommended (Level II recommendation), but not overly emphasized within the first 6 h after symptom onset. (7) Follow the diagnostic process outlined in the above guidelines (Level I recommendation).

ii. General Management

Currently, there is limited high-grade study evidence on general management; consensus recommendations are as follows.

- (i) Oxygen Therapy and Respiratory Support
- (1) Patients with concomitant hypoxemia (oxygen saturation below 92% or arterial blood gas indicating hypoxia) should receive oxygen therapy. Those with severe airway obstruction should receive airway support (endotracheal intubation or tracheostomy) and assisted ventilation. (2) Patients without hypoxemia do not require routine oxygen therapy.
- (ii) Cardiac Monitoring and Management of Cardiac Abnormalities

